8.2.3.2. Safety Holding Rules

The safety holding rules for the vaccination phases of the study are defined in Table 14.

For participants enrolled in Step 1, holding rules 1a-1d from Table 14 will be assessed by the investigator on a continuous basis, and meeting any of these holding rules will trigger a hold of vaccination irrespective of number of participants enrolled and/or timing of the event relative to

vaccination. Holding rules 2a-2c from Table 14 will be assessed by the iSRC during the safety evaluations on unblinded data.

These holding rules have been written under the assumption that the safety data from all participants will be available. If the data from all Step 1 participants are not available (i.e., in case a participant is lost to follow-up), then the holding rules will be assessed on a pro-rata basis (expressed as percentage of participants to be evaluated) i.e., 3 out of 12 participants per arm or 25% per arm.

Of note, no formal holding rules will be applied for other safety data such as non-life-threatening SAEs, missed visits due to study intervention-related AEs, Grade 1 and Grade 2 solicited and unsolicited AEs in the 7-day follow-up period and unsolicited AEs collected from Day 8 to Day 30 after study intervention administration. However, if available, these data will also be reviewed by the iSRC to allow an overall assessment of the benefit/risk ratio of study intervention administration.

If the investigator becomes aware of a holding rule being met, they must suspend administration of the study intervention and inform IQVIA immediately (e.g., holding rules 1a-d). IQVIA will inform the investigator if holding rules 2a-c are met. Investigators will be responsible to inform the IRB/IEC if a holding rule has been met.

The following communication sequence must be followed:

- The concerned site staff will put study intervention administration and enrollment on hold.
- The concerned site staff will immediately inform IQVIA's safety team (i.e., the events to be reported via an Electronic Data Capture system [EDC]).
- Enrollment and intervention allocation through IVRS/IWRS will then be stopped on a study level.
- IQVIA will inform all investigators about the stopping of enrollment and intervention.
- IQVIA will also provide the blinded data to GSK's Clinical Research and Development Lead and Safety Lead for further SRT and GSK Global Safety Board review.

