8.3.1. Time Period and Frequency for Collecting AEs/SAEs, pIMDs, and Pregnancy Information

Collection of AEs, SAEs, pregnancies, and pIMDs will be performed at the time points and periods specified in Table 15.

Medical occurrences that begin before the start of study intervention but after obtaining informed consent will be recorded on the medical history section of the eCRF, not the AE section.

All SAEs will be recorded and reported to IQVIA within 24 hours. The investigator will submit any updated SAE data to IQVIA within 24 hours of it being available through the Expedited Report Form.

Investigators are not obligated to actively seek AE or SAE after the participant concluded the study participation. However, if the investigator learns of any SAE, including a death, at any time after the participant has been discharged from the study, and the event is considered reasonably related to the study intervention, the investigator must notify IQVIA.

Table 15 Time Period and Frequency for Collecting AE/SAE and Pregnancy Information

	Visit 1	Visit 2		Visit 3		Visit 4	Visit 5		Visit 6	Visit 7
	Day 1	Day 7		Month 2		Month 3	Month 6		Month 7	Month 12
Event	Dose 1	7 days post- Dose 1	28 days post- Dose 1	Dose 2	7 days post- Dose 2	28 days post- Dose 2	Dose 3	7 days post- Dose 3	28 days post- Dose 3	Study conclusion
Administration site and systemic solicited events										
Unsolicited AEs										
SAEs (all, fatal, related)										
pIMDs										
AEs/SAEs leading to withdrawal from the study										
SAEs related to study participation or concurrent GSK										
medication/vaccine Pregnancies/pregnancy outcomes										

AE = adverse event; SAE = serious adverse event; pIMD = potentially immune-mediated disease

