8.3.8. Medical Device Deficiencies

This clinical study will collect information of any device deficiencies associated with the study interventions that are combination products. Refer to Glossary of Terms for the definition of a combination product and a medical device deficiency.

¹ Timeframe allowed after receipt or awareness of the information by the investigator/study center staff.

² The investigator will confirm review of the SAE/pIMD causality by ticking the "reviewed" box in the electronic Expedited AE Report within 72 hours of submission of the SAE/pIMD.

³ For coronavirus disease 2019 (COVID-19) related SAEs, reports should be submitted following routine procedures for SAEs.

⁴ Timeframe allowed once the investigator determines that the event meets the protocol definition of an pIMD.

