Follow-up After the Participant is Discharged from the Study

The investigator will provide any new or updated relevant information on previously reported SAE to IQVIA using electronic Expedited AE Report as applicable. The investigator is obliged to perform or arrange for the conduct of supplemental clinical examinations/tests and/or evaluations to elucidate the nature and/or causality of the AE or SAE as fully as possible.

Updating of SAE, pIMD, Pregnancy Information After Removal of Write Access to the Participant's eCRF

When additional SAE, pIMD, and pregnancy information is received after removal of write access to the participant's eCRF, new or updated information should be recorded on the appropriate paper report, with all changes signed and dated by the investigator. The updated report should be faxed to IQVIA within the timeframe specified in Table 16.

Follow-up of Pregnancies

Pregnant participants will be followed to determine the outcome of the pregnancy. At the end of the pregnancy, whether full-term or premature, information on the status of the mother and child will be forwarded to IQVIA using the pregnancy follow-up report and the Expedited AE Report if applicable. Generally, the follow-up period does not need to be longer than 6 to 8 weeks after the estimated date of delivery.

Regardless of the reporting period for SAEs in this study, if the pregnancy outcome is an SAE, it should always be reported as such.

Furthermore, if the investigator becomes aware of any SAE occurring as a result of a post-study pregnancy AND it is considered by the investigator to be reasonably related to the study intervention, they must report this information to IQVIA.

Events Requiring Expedited Reporting to IQVIA

Once an investigator becomes aware that an SAE has occurred in a study participant, the investigator or investigator's designee must complete information in the electronic Expedited AE Report WITHIN 24 HOURS. The report will always be completed as thoroughly as possible with all available details of the event. The report allows to specify that the event is serious or non-serious.

Even if the investigator does not have all information regarding an SAE, the report should still be completed WITHIN 24 HOURS. Once additional relevant information is received, the report should be updated WITHIN 24 HOURS. The investigator will always provide an assessment of causality at the time of the initial report.

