The investigator will be required to confirm the review of the SAE causality by ticking the "reviewed" box in the electronic Expedited AE Report within 72 hours of submission of the SAE.

Refer to Table 15 for the details on timeframes for reporting of SAEs.

SAE Reporting to IQVIA via EDC

- The primary mechanism/tool for reporting an SAE to IQVIA will be the EDC.
- If the EDC is unavailable for more than 24 hours, then the study center will use the paper Expedited AE Report.
- The study center staff will enter the SAE data into the EDC as soon as it become available.
- After the study is completed at a given site, the EDC will be taken offline to prevent the entry of new data or changes to existing data.
- If a study center receives a report of a new SAE, pIMD, pregnancy from a participant or receives updated data on a previously reported SAE after the EDC has been taken offline, then the study center can report this information on a paper Expedited AE Report (see the next section) or to the Medical Monitor by phone.

Contacts of the Medical Monitor for SAE reporting can be found in the SRM.

Back-up SAE Reporting to IQVIA via Paper (in Case of EDC Failure)

- Fax transmission of the SAE paper Expedited AE Report is the preferred method to transmit this information to the Medical Monitor.
- In rare circumstances and in the absence of fax equipment, notification by phone is acceptable with a copy of the Expedited AE Report sent by overnight mail or courier service.
- Initial notification via phone does not replace the need for the investigator to complete and sign the Expedited AE Report within the designated reporting timeframes.

Contacts of the Medical Monitor for SAE reporting can be found in the SRM.

Adverse Events Related to the Use of Medical Devices

Definitions of a Medical Device AE and Adverse Device Effect

- A medical device AE is any untoward medical occurrence, in a clinical study participant, users, or other persons, temporally associated with the use of study intervention whether or not considered related to a medical device. An AE can therefore be any unfavorable and unintended sign (including an abnormal laboratory finding), symptom, or disease (new or exacerbated) temporally associated with the use of a medical device. This definition includes events related to the medical device or comparator and events related to the procedures involved.

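### The paper back-up for SAE reports is triggered only by an EDC outage of more than 24 hours, so it can open after the protocol's own 24-hour reporting limit has passed

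*Protocol*

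**What the plan says.** The reporting limit appears in several places in the protocol. Section 8.3.1: "All SAEs will be recorded and reported to IQVIA within 24 hours". Table 16 (Section 8.3.5) gives 24 hours for an initial SAE report, and its footnote 1 starts the clock at the site: "Timeframe allowed after receipt or awareness of the information by the investigator/study center staff". In Appendix 4, under Events Requiring Expedited Reporting to IQVIA, the investigator or designee "must complete information in the electronic Expedited AE Report WITHIN 24 HOURS", and incomplete information is no reason to wait: "Even if the investigator does not have all information regarding an SAE, the report should still be completed WITHIN 24 HOURS". None of these places extends the limit for EDC downtime.

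The back-up is in the next part of Appendix 4, SAE Reporting to IQVIA via EDC: "If the EDC is unavailable for more than 24 hours, then the study center will use the paper Expedited AE Report". The section after that, on paper back-up, makes fax the preferred method. It then adds: "In rare circumstances and in the absence of fax equipment, notification by phone is acceptable", with a copy of the report to follow by overnight mail or courier. It closes off the phone call as a substitute: "Initial notification via phone does not replace the need for the investigator to complete and sign the Expedited AE Report within the designated reporting timeframes".

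For the holding rules, the communication sequence in Section 8.2.3.2 says: "The concerned site staff will immediately inform IQVIA's safety team (i.e., the events to be reported via an Electronic Data Capture system [EDC"). The step that follows is the stop of enrollment and allocation at study level.

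Appendix 4 sends the reader to Table 15 for SAE reporting timeframes. Table 15 covers collection periods. The reporting timeframes are in Table 16.

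**The concern.** A back-up route exists so that a deadline can be met when the main route fails. Here the condition for using it is as long as the deadline. A site that knows of an SAE, finds the EDC down and follows the stated trigger can be carried past the limit by the protocol's own instruction. The next section then still holds it to that limit.

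The holding-rule notice has a related gap. A single event meets any of rules 1a to 1d (Table 14), the notice is due at once, and the only route named in the communication sequence is the EDC. If the EDC is down, that section does not say how the notice reaches IQVIA, and the study-level stop comes after the notice.

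At stake are timely expedited safety reporting for all participants until study end and, in Step 1, prompt action at sites other than the one that saw the event.

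**Working it through.** The plan gives no figure to reproduce. The check is a comparison of two clocks.

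**Inputs**
- Reporting limit: 24 h from site awareness (Section 8.3.1; Table 16 with footnote 1; Appendix 4).
- Stated trigger for paper: EDC unavailable for more than 24 h (Appendix 4).
- Allowance for downtime: none stated.
- Effect of a phone call on the limit: none (Appendix 4, paper back-up section).

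**Set-up.** Put site awareness at hour 0 and let the outage start at hour *s*, negative if it began before awareness.
- Report due: hour 24.
- Paper trigger met: after hour *s* + 24.
- Time left when paper opens: 24 − (*s* + 24) = −*s* hours.

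| Outage starts | Paper opens after | Time left to the limit |
|---|---|---|
| 6 h before awareness (*s* = −6) | hour 18 | 6 h |
| at awareness (*s* = 0) | hour 24 | none |
| 6 h after awareness, report not yet filed (*s* = +6) | hour 30 | 6 h late |

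The limit is therefore missed under the stated trigger when three things hold together: the outage starts at or after awareness, the report has not yet been filed, and the outage lasts to hour 24. If the EDC returns before hour 24, the electronic report can still be on time. If the outage began before awareness, some time remains.

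The outage need not itself exceed 24 h. With *s* = +6 it needs to last only 24 − 6 = 18 h to reach the deadline, and at that point the paper trigger has not been met.

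**Holding-rule notice.** This is due immediately, so about hour 0. If the outage is already running and less than 24 h old, the EDC route is closed until the EDC returns. If the Appendix 4 trigger is carried over, paper opens after *s* + 24 hours: 18 h for *s* = −6, and 24 h at most, for *s* = 0. This is the delay in the named channel. It is not necessarily the delay in the notice, because other duties of contact apply.

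**The case against.** The strongest reply is that the protocol never forbids earlier use of paper. The sentence says what sites will do after more than 24 hours and does not contain the word only. The heading of the paper section refers to EDC failure with no threshold. Appendix 2, Data Quality Assurance, likewise provides for a printed case report form if the EDC fails, again with no threshold. Since the report must in any case meet the designated timeframe, a sensible site could read the text as allowing paper earlier. This stands in part: a reader might infer that no written route is permitted in the first 24 hours, and the documents do not say that. It does not remove the conflict, because the outage of more than 24 hours is the only trigger stated while the study is running at a site. The separate paper-or-phone option applies after the EDC has been taken offline at study completion.

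On the holding rules, the reply is stronger. The first step in Section 8.2.3.2 is the site's own hold, which does not use the EDC. The paragraph before the sequence requires the investigator to suspend administration and inform IQVIA immediately, with no channel named. Section 8 also asks that immediate safety concerns be discussed with IQVIA as soon as they occur. Medical Monitor contacts are in the Study Reference Manual, which is not among the documents. All of this stands. What remains is that the sequence names one channel and no back-up to it.

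A reader might also infer that the 60-minute spacing between Step 1 participants is defeated. It is not: Section 4.1 ties that spacing to the ability of sites to put vaccination on hold, and the site hold is unaffected. Nor can a number of Step 1 participants dosed during a delay be derived. The documents give no clinic hours or EDC outage rates, and do not say whether the spacing runs per site or across the study. Under the current version, Step 1 first dosing was evidently complete. Amendment 3 applies its Month 2 change to samples already collected, Appendix 3 places those participants in Step 2, and Step 2 could start only after all 48 Step 1 participants had been enrolled and reviewed.

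**Conclusion.** The point holds as an internal conflict between a stated trigger and a stated limit. A site that follows the paper trigger literally reports an SAE late whenever the outage starts at or after awareness, before filing, and lasts to the deadline. For an outage starting *s* hours after awareness, paper opens only after the limit has been passed by *s* hours. How often this would happen cannot be estimated, because the documents give nothing on EDC reliability. The conclusion rests on the text alone and on reading the trigger as sites are likely to follow it.

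The conflict covers all participants to study end. The holding-rule part is narrower: it concerns the missing back-up channel in Section 8.2.3.2, belongs to Step 1, and affects the notice that precedes the study-level stop, not the reporting site's own hold. The Table 15 reference is a plain cross-reference error.

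The analysis is not affected. The SAE endpoint in SAP Section 17.1.3.3 counts participants with an event, and a report that arrives some hours late does not change that count. The change is worth making because the stated rule can breach the protocol's own safety limit and the correction is nearly free.

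**What to change.** Reconcile the passages as follows.

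1. In Appendix 4, SAE Reporting to IQVIA via EDC, delete the condition on an outage longer than 24 hours. State that if the EDC is unavailable when a report is due, the study center uses the paper Expedited AE Report (by fax, or by phone followed by paper) in time to meet the timeframe in Table 16.
2. In Section 8.2.3.2, add a cross-reference to this back-up route at the step where site staff inform IQVIA's safety team.
3. In Appendix 4, Events Requiring Expedited Reporting to IQVIA, change the reference for SAE reporting timeframes from Table 15 to Table 16.

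The cost is wording only. The paper form, fax and phone routes are already in place. Device deficiency reports, also due within 24 hours, already go by fax with no outage threshold, so the protocol has a model for the revised text.

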APPENDIX 5 CONTRACEPTIVE GUIDANCE AND COLLECTION OF PREGNANCY INFORMATION

Definitions

Woman of Childbearing Potential

A woman is considered fertile following menarche and until becoming postmenopausal unless permanently sterile (see below).

Women of Non-Childbearing Potential

Premenarchal

Menarche is the first onset of menses in a young woman. Menarche is normally preceded by several changes associated with puberty including breast development and pubic hair growth.

Additional evaluation should be considered if a participant's fertility status is unclear (e.g., amenorrhea in adolescents or athletes) and a menstrual cycle cannot be confirmed before first dose of study intervention.

- Premenopausal woman with ONE of the following:
 - Documented hysterectomy
 - Documented bilateral salpingectomy
 - Documented bilateral oophorectomy

Note: Documentation can come from the site personnel's: review of participant's medical records, medical examination, or medical history interview.

• Postmenopausal woman

A postmenopausal state is defined as no menses for 12 months without an alternative medical cause. A high follicle stimulating hormone (FSH) level in the postmenopausal range may be used to confirm a postmenopausal state in women not using hormonal contraception or hormonal replacement therapy (HRT). However, in the absence of 12 months of amenorrhea, a single FSH measurement is insufficient.

Women on HRT and whose menopausal status is in doubt will be required to use a
non-hormonal, highly effective contraception method if they wish to continue their HRT
during the study. Otherwise, they must discontinue HRT to allow confirmation of
postmenopausal status before study enrollment.

Contraception Guidance

Female participants of childbearing potential are eligible to participate if they agree to use a highly effective contraceptive method consistently and correctly according to the methods listed in GSK's list of highly effective contraceptive methods (Table 22).

Table 22 Highly Effective Contraceptive Methods

Highly Effective Contraceptive Methods That Are User Dependent* Failure rate of <1% per year when used consistently and correctly

Combined (estrogen- and progestogen-containing) hormonal contraception associated with inhibition of ovulation

- Oral
- Intravaginal
- Transdermal

Progestogen-only hormonal contraception associated with inhibition of ovulation

- Injectable
- Oral

Highly Effective Methods That Are User-Independent

- Implantable progestogen-only hormonal contraception associated with inhibition of ovulation
- Intrauterine device
- Intrauterine hormone-releasing system
- Bilateral tubal occlusion

Vasectomized partner

A vasectomized partner is a highly effective contraception method provided that the partner is the sole male sexual partner of the female participant of childbearing potential and the absence of sperm has been confirmed. If not, an additional highly effective method of contraception should be used.

Male partner sterilization prior to the female participant's entry into the study, and this male is the sole partner for that participant,

The information on the male sterility can come from the site personnel's review of the participant's medical records; medical examination and/or semen analysis, or medical history interview provided by her or her partner.

Sexual abstinence

Sexual abstinence is considered a highly effective method only if defined as refraining from heterosexual intercourse during the entire period of risk associated with the study drug. The reliability of sexual abstinence needs to be evaluated in relation to the duration of the study and the preferred and usual lifestyle of the participant.

Female Participants who Become Pregnant

Refer to Section 8.3 and Appendix 4 for the information on detection, recording, reporting and follow-up of pregnancies.

Any female participant who becomes pregnant during the study will need to discontinue further vaccination but may continue other study procedures at the discretion of the investigator.

^{*}Typical use failure rates may differ from those when used consistently and correctly. Use should be consistent with local regulations regarding the use of contraceptive methods for participants in clinical studies.

APPENDIX 6 PROTOCOL AMENDMENT HISTORY

The Protocol Amendment Summary of Changes Table for the current amendment is located directly before the table of contents.

Protocol Amendment 2: 23 September 2022

This amendment is considered to be substantial based on the criteria set forth in Article 10(a) of Directive 2001/20/EC of the European Parliament and the Council of the European Union.

Overall Rationale for Amendment

The purpose of the Protocol Amendment 2 is to allow for additional iSRC review(s) in case of enrollment delay to mitigate the risk that the iSRC for all 48 Step 1 participants may occur after the allowed interval range for their second vaccination dose. Additionally, the country-specific amendment for Germany (Protocol Amendment 1/DEU-1) to clarify that only adults between and including 18 to 26 years of age will be included in the study in Germany was incorporated. Further updates (as summarized below) were made to clarify the study procedures.

Added text is **bold italic** and deleted text is strikethrough.

Section and Name	Description of Change	Brief Rationale
1.1. Synopsis 4.1 Overall Design 8.2.3.3 iSRC Evaluation	*In case not all 48 of the Step 1 participants are enrolled and vaccinated with a first dose of study vaccine by 30 September 2022, the iSRC will review the accumulated safety data up to 7 days post-dose 1 of all participants available by that date. If no safety signal is identified, these participants will be vaccinated with a second dose. To avoid any additional participants running out of the allowed interval range for their second vaccine dose, additional iSRC review(s) may need to be planned to review the safety data up to 7 days post-dose 1 of these participants, but only when all 48 Step 1 participants have been enrolled and their data have been reviewed by the iSRC, the iSRC will decide on the initiation of the vaccination of Step 2 participants.	To allow for additional iSRC review(s) in case of enrollment delay to mitigate the risk that the iSRC for all 48 Step 1 participants may occur after the allowed interval range for their second vaccination dose.
1.1. Synopsis	In Overall Design, the note was added: Vaccination of Step 2 participants with a second dose will not be	Clarification to the study protocol

Section and Name	Description of Change	Brief Rationale
	initiated before all Step 1 participants have received their second vaccination dose.	
8.2.3.3 iSRC Evaluation	Edited text: Following this first initial review(s), the iSRC will review all available safety data on a regular basis (monthly) until data from 1-month post-dose 2 for all participants and data from 1-month post-dose 3 for Step 1 participants are reviewed.	Clarification to the procedures associated with iSRC review
1.3 Schedule of Activities	Added footnote: ² Blood samples should be collected prior to vaccine administration. The footnotes were renumerated accordingly along with the associated bookmarks.	Clarification of study procedures order
4.1 Overall Design	Figure 1: Updated Solicited events (7 days) and Unsolicited events (28 days) by moving from Visit 6 to Visit 5.	Correction to align with study procedures
6.1 Study Interventions Administered	Footnote added to Table 6: *The nondominant arm is the preferred arm of injection. In case it is not possible to administer the vaccine in the nondominant arm, an injection in the dominant arm may be performed.	Clarification to allow for flexibility in the laterality of study vaccines administration
8.2.1.3 Physical Examination/Vital Signs	On Day 1, a history directed physical examination will be performed for each participant. On Day 1, a history directed physical examination (including the injection site examination) will be performed for each participant as per the standard of care.	Clarification of study procedure.
Summary of Changes	Summary of Changes table was added to document the most recent updates made to the protocol.	Version control
Appendix 6	Appendix 6 was added to include the previous history of changes to the protocol. The Signature of Investigator was moved to Appendix 7.	Version control
Global document updates	Minor clarifications, grammar corrections, version updates have been made.	Minor edits are not summarized.
1.1 Synopsis	The note added:	

Section and Name	Description of Change	Brief Rationale
1.3. Schedule of Activities 4.1. Overall Design 5.1. Inclusion Criteria	In Germany, only adult participants between and including 18 years to 26 years of age are to be included in this clinical study.	Revision to address the request of health authority of Germany
2.2. Study Rationale4.2.2. Selection of Study Population	The note added: (18-26 years of age in Germany)	

Protocol Amendment 1/DEU-1: 23 June 2022

This amendment is considered to be substantial based on the criteria set forth in Article 10(a) of Directive 2001/20/EC of the European Parliament and the Council of the European Union.

This amendment applies only to Germany.

Overall Rationale for the Amendment:

This is a country-specific amendment for Germany to clarify that only adults between and including 18 to 26 years of age will be included in the study in this country.

Added text is **bold italic**

Section # and Name	Description of Change	Brief Rationale
1.1 Synopsis1.3. Schedule of Activities4.1. Overall Design5.1. Inclusion Criteria	The note added: In Germany, only adult participants between and including 18 years to 26 years of age are to be included in this clinical study.	Revision to address the request of health authority
2.2. Study Rationale4.2.2. Selection ofStudy Population	The note added: (18-26 years of age in Germany)	

Protocol Version 2.0: 02 March 2022

Overall Rationale for the Protocol Version 2.0

The purpose of the Protocol Version 2.0 is to increase the volume of blood sample collected for antibody determination to enable the development and quantification of laboratory assays. Further, several clarifications of the study procedures as summarized below are included.

Added text is **bold italic** and deleted text is strikethrough.

Section # and Name	Description of Change	Brief Rationale
1.3 Schedule of Activities	Added activity to Visits 1, 3, and 5: Distribute and instruct participants/participant's parent(s)/LAR(s) on the use of Memory Aid for unsolicited AEs and concomitant medication/vaccination	Clarification of study procedures
	Added activity to Visits 3, 4, and 6: Return of Memory Aids	Clarification of study procedures
1.3 Schedule of Activities (Table 1) 8.1.1 Biological Samples Table 7	Blood sampling for antibody determination (~20 50 mL)	Higher volume of blood sample is needed for laboratory assays development and qualification
1.3 Schedule of Activities (Table 1 and Table 2) 8.1.1 Biological Samples (Table 7)	Footnote added for Visit 2**: ** Visit 2 is for Step 1 participants only	Clarification of study procedures
4.1 Overall Design	Edited Figure 1 Footnote: *iSRC reviews Sentinel participants post-dose 1 safety data, then iSRC reviews the data on monthly basis until safety data from one I-month post-dose 2 for all participants and data from 1- month post-dose 3 for Step 1	Clarification of data reviewed by the iSRC
6.3.2 Randomization to Study Intervention	The study and the center will be used as a minimization factor for randomization in Step 1 and the study, the center and will be used as a minimization factor for randomization in Step 2.	Clarification of minimization factors for randomization

6.8 Concomitant Medications/Products and Concomitant Vaccinations	Memory aids used by participant/participant's parent(s)/LAR(s) will be reviewed for any additional medication(s) and vaccination(s), which will be transcribed in eCRFs.	Clarification of study procedures
8.2.2.3 iSRC Evaluation	Following this first review, the iSRC will review all available safety data on a regular basis (monthly) until data from 1-month post-dose 2 for all participants and data from 1-month post-dose 3 for Step 1 participants are reviewed.	Clarification of data reviewed by the iSRC
8.3.2 Method of Detecting AEs and SAEs, Pregnancies, and pIMDs	Memory aids used by participant/participant's parent(s)/LAR(s), will be reviewed for health-related issues of participants and for potential AEs, which will be transcribed in eCRFs.	Clarification of study procedures
9.4.3 iSRC Analyses	The analysis will be based on the ES. The analyses will be further described in detail in the statistical analysis plan. Demographic characteristics, baseline general medical and vaccination history, withdrawals from the study. [] Summary tables containing information on any events considered in the holding rules and other events (SAE, any withdrawal due to intervention-related AE, any AEs causing study-withdrawal from the study). Incidence of solicited local administration site AEs (pain, redness, swelling): any grade, Grade 3 (2 -day period days or more after Dose 1, 7-day follow-up period after intervention), any solicited administration site AEs leading to hospitalization within 7 days (Day 1 - Day 7) after each vaccine dose. Incidence of solicited general AEsystemic AEs (fever, headache, fatigue, myalgia, and arthralgia): any grade, Grade 3, any related, Grade 3 related (2 days or more after Dose 1, 7-day follow-up period after each intervention), any solicited systemic AEs leading to hospitalization, fever >40°C (104°F), within 7 days (Day 1 - Day 7) after each vaccine dose). []	Clarification of the analyses performed for the iSRC to align with the iSRC charter

	Any, Grade 3 or above abnormality in pre-specified hematology and biochemistry parameters with an event onset within 7 days (Day 1 – Day 7) after each vaccine dose.	
	Incidence of SAEs: Any, any related, fatal, fatal related.	
	Incidence of pIMDs: Any, any related.	
	[]	
	Any pregnancy and pregnancy outcomes, overall and pregnancy exposures (i.e., exposures during pregnancy).	
	[]	
	Safety narratives, patient profiles and laboratory reports, if required.	
	Other information as deemed necessary by the iSRC.	
Global document updates	Minor clarifications, grammar corrections, version updates have been made to this document.	Minor edits are not summarized.

